5.7.3 Target volumes, margins, and compliance criteria

The structures marked as “Required” in the table must be contoured and documented in the Radiation Oncology Treatment Plan.

Conventional RT (4-field box)

For a 4-field box treatment without 3D planning, contouring target volumes is not required. For 3D plans, target volumes and margins will be the same as for IMRT described below. The only difference between 3D plans and IMRT contours is that patients treated with 3D planning will not have an ITV option.

IMRT

Pelvic MRI and/or PET fusion with the CT simulation scan is recommended to aid target delineation. Fusion should be optimized to match the MRI/PET scans to the treatment position. The Gross Tumor Volume (GTV), Clinical Target Volume (CTV) and Planning Target Volume

BrUOG 355: 7/8/17, 7/11/17, 7/20/17, 8/7/17, 8/8/17, 8/14/17, 8/16/17, 8/21/17, 8/22/17, 8/24/17, 8/28/17, 9/5/17, 9/6/17, 9/8/17, 9/11/17, 11/7/17, 11/8/17, 11/19/17 approved DD, 11/20/17, 12/12/17, 12/14/17, 1/29/18, 2/1/18, 2/6/18, 2/7/18, 2/8/18, 2/9/18, 2/12/18, 2/13/18, 3/8/18 all reviews, 3/9/18, 3/13/18, 3/14/18, 3/15/18, 4/19/18, 4/23/18, 5/29/18, 6/5/18, Amendment # 1 7/9/18, Amendment # 2 12/12/18, Amendment #3, 4/6/2020, Amendment #4 5/11/2020

(PTV) will be contoured on all CT slices in which the structures exist.

Standard	Description	Specification
Gross Tumor Volume (GTV)	Required dose = 45 Gy	The GTV is defined as all known gross disease determined from radiographic studies, clinical information, physical examination, endoscopic examination, and biopsy results.
Cervical Tumor Volume (CTV)	Required dose = 45 Gy	The CTV will be divided in to 3 sub regions: CTV1, CTV2, CTV3. CTV1 will consist of the gross tumor, cervix, and uterus. CTV2 will consist of the parametria and superior third of the vagina (or half of the vagina, if the vagina is clinically involved). CTV3 will include the common, external, and internal iliac and presacral lymph nodes. The upper border of the CTV3 should not extend above the confluence of the common iliac arteries with the aorta (i.e., aortic bifurcation), and should begin no lower than superior border of L5. The nodal CTV (CTV3) will be obtained by ensuring an approximately 7 mm margin around the vessels, plus extension to include any adjacent visible lymph nodes, lymphoceles, or pertinent surgical clips. The presacral nodes should be contoured until the superior border of the S3 vertebral body is reached; below this point the nodal volume can be separated into two structures. The external iliac nodes should be contoured to the superior aspect of the femoral head. CTV3 should be modified to exclude bone, muscle, and bowel. The CTV should not extend inferior to the ischial tuberosities.

BrUOG 355: 7/8/17, 7/11/17, 7/20/17, 8/7/17, 8/8/17, 8/14/17, 8/16/17, 8/21/17, 8/22/17, 8/24/17, 8/28/17, 9/5/17, 9/6/17, 9/8/17, 9/11/17, 11/7/17, 11/8/17, 11/19/17 approved DD, 11/20/17, 12/12/17, 12/14/17, 1/29/18, 2/1/18, 2/6/18, 2/7/18, 2/8/18, 2/9/18, 2/12/18, 2/13/18, 3/8/18 all reviews, 3/9/18, 3/13/18, 3/14/18, 3/15/18, 4/19/18, 4/23/18, 5/29/18, 6/5/18, Amendment # 1 7/9/18, Amendment # 2 12/12/18, Amendment #3, 4/6/2020, Amendment #4 5/11/2020

CTV (for SIB schemes)	Required dose = 47.6 Gy	Same as above
CTVn boost (for boost)	Required dose = 54.0 to 59.4 Gy	Gross pelvic nodes
ITV	Total dose = 45 Gy	Patients should be simulated with both a full and empty bladder (i.e., 2 simulation scans). CTV1-CTV3 and PTV1-PTV3 should be delineated as described above on the plan used for treatment (either the full or empty bladder scan), and CTV1 should be delineated on both scans. The CTV1 from both scans should be fused together to generate the ITV. A 7 mm margin should be applied to generate PTV4. PTV4 should be fused with PTV1-PTV3 to generate the final PTV.
Pelvic Tumor Volume (PTV)	Required dose = 45 Gy	Around CTV1, a 15 mm uniform expansion should be used. Around CTV2, a 10 mm uniform expansion should be used. Around CTV3 (and CTV_boost, if applicable), a 5 mm uniform expansion should be used. These expansions will generate PTV1, PTV2, and PTV3, respectively. PTV1-3 will be fused to generate the PTV .
PTV-skin	IF applicable only: PTV-3mm from skin surface	The PTV should be manually or automatically trimmed up to 3 mm from the skin surface, if necessary, to spare skin. However, the CTV still needs to be included entirely within the PTV .
PTV-boost	Required dose = 54 to 59.4 Gy	5 mm uniform expansion around CTV_Boost

Brachytherapy (point-directed)

The definition of all points (A, B, Bladder, Rectum and Vaginal Surface) will be in accordance with the 1985 ICRU Report #38: Dose and Volume Specifications for Reporting Intracavitary Therapy in Gynecology.

BrUOG 355: 7/8/17, 7/11/17, 7/20/17, 8/7/17, 8/8/17, 8/14/17, 8/16/17, 8/21/17, 8/22/17, 8/24/17, 8/28/17, 9/5/17, 9/6/17, 9/8/17, 9/11/17, 11/7/17, 11/8/17, 11/19/17 approved DD, 11/20/17, 12/12/17, 12/14/17, 1/29/18, 2/1/18, 2/6/18, 2/7/18, 2/8/18, 2/9/18, 2/12/18, 2/13/18, 3/8/18 all reviews, 3/9/18, 3/13/18, 3/14/18, 3/15/18, 4/19/18, 4/23/18, 5/29/18, 6/5/18, Amendment # 1 7/9/18, Amendment # 2 12/12/18, Amendment #3, 4/6/2020, Amendment #4 5/11/2020

Brachytherapy (volume-directed)

The MRI based target delineation can be reused by superimposition in the process of contouring on CT, if for subsequent fractions of brachytherapy only CT can be used with the applicator in place. No planning margins will be added to the CTV.

Standard name	Description	Specification
GTV	Required dose = 27.5-30 Gy	Macroscopic tumor (if present) at time of brachytherapy
CTV		GTV + whole cervix + presumed extra cervical tumor extension

Compliance criteria:

	Per protocol	Variation (Acceptable)	Deviation (Unacceptable)*
Overall Treatment time	≤ 60 days	≤ 66 days	>66 days

Patients who require a treatment delay of RT for 7 consecutive days or longer will be removed from this protocol. The decision to continue standard chemoradiation will be left to the treating physician. See Section 6.2.

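### For contoured plans, the target-volume table in 5.7.3 gives extended-field patients no elective para-aortic target, contrary to 5.6, 5.7 and 5.7.2

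*Combined protocol and SAP*

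**What the plan says.** Section 5.7.3 has one target table for contoured treatment. It is written for IMRT and extended to 3D planning: "For 3D plans, target volumes and margins will be the same as for IMRT described below". A four-field box set up without 3D planning is outside it: "For a 4-field box treatment without 3D planning, contouring target volumes is not required".

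Within the table:

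- **Nodal CTV.** "CTV3 will include the common, external, and internal iliac and presacral lymph nodes". Its top is limited: "The upper border of the CTV3 should not extend above the confluence of the common iliac arteries with the aorta (i.e., aortic bifurcation".
- **PTV.** "Around CTV3 (and CTV_boost, if applicable), a 5 mm uniform expansion should be used", and "PTV1-3 will be fused to generate the PTV".
- **ITV option.** "PTV4 should be fused with PTV1-PTV3 to generate the final PTV". PTV4 is derived from CTV1, so it adds no nodal region.
- **SIB row.** It repeats the CTV definition at a different dose.
- **Boost row.** The boost CTV is limited to "Gross pelvic nodes".

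Elsewhere the protocol describes the extended field differently:

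- 5.6 pairs involved para-aortic nodes with a field covering the pelvis and the para-aortic region.
- 5.7 defines the Cohort 1A field by a superior border above L4-L5, whatever the technique, and refers to 5.7.1 for detail.
- 5.7.1 sets that border 3 cm or more beyond the highest gross node, in a list that applies when bone landmarks are used.
- 5.7.2, under its IMRT heading, includes the para-aortic regions for extended fields, with a margin of at least 2 cm.

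**The concern.** Extended-field radiation is one of the two fields named in the first primary objective (1.2.1), and it defines Cohort 1A as labelled in 5.4 and 5.7 (16.3 reverses the 1A and 1B labels). What separates it from whole-pelvic treatment is coverage above the pelvis. A planner who contours from the 5.7.3 table would produce a PTV that stops close to the aortic bifurcation, which is in substance a whole-pelvic target.

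The PTV is not only a label. In 5.7.5 the IMRT dose is prescribed to it, and in 5.7.4 the bowel contour starts 1 cm above its highest slice. A PTV that leaves out the para-aortic region therefore carries through to dose coverage and to the bowel volume assessed. It would also blur what the extended-field toxicity results describe, because some patients counted in that group might not have received the field.

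**Working it through.** The protocol gives no statistical figure on this point. The check sets the sections side by side and counts the patients concerned.

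**1. Does any row of the 5.7.3 table supply an elective para-aortic target?**

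| Row | Content | Elective para-aortic target? |
|---|---|---|
| GTV | Known gross disease, 45 Gy | No. It could hold a gross para-aortic node, but PTV1 to PTV3 are not built from the GTV row |
| CTV1 | Gross tumour, cervix, uterus | No |
| CTV2 | Parametria, upper vagina | No |
| CTV3 | Iliac and presacral nodes, capped at the bifurcation | No |
| CTV for SIB | Same as the CTV row | No |
| CTVn boost | Gross pelvic nodes | No |
| ITV / PTV4 | From CTV1 | No |
| PTV | PTV1 + PTV2 + PTV3 | No |

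The 5 mm expansion around CTV3 adds only 5 mm above the cap. CTV3 may be extended to adjacent visible nodes, but that concerns nodes that are seen, not an elective region. No row mentions an extended field.

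**2. What do the other sections require of a contoured extended-field plan?**

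- 5.6 applies to all patients: pelvis and para-aortic region when para-aortic nodes are involved.
- 5.7 applies to Cohort 1A without limit by technique: superior border above L4-L5.
- 5.7.2 stands under the IMRT heading: para-aortic regions included, minimum margin 2 cm.

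5.6 and 5.7.2 name the para-aortic region, which lies above the bifurcation and so above the cap. The conflict with them does not depend on where the highest gross node lies.

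**3. Does any text settle which section prevails?**

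- 5.7 sends the reader to 5.7.1. There the 3 cm rule falls under the bone-landmark option, and 3D planning with explicit targets is sent to section 5.2.3, which does not exist. Target volumes are in 5.7.3, the table that lacks the row.
- 5.4 lets the treating radiation oncologist choose the field. It does not define the contours.
- 5.7.5 mentions 45 Gy by either field but sets no para-aortic target.

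No precedence is stated.

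**4. How many patients?**

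- Cohort 1: 4 planned per field group (5.4), so 4 extended-field patients. 4 / 24 = 16.7%. The protocol does not say how many will have contoured plans, so the number affected is 0 to 4.
- Cohorts 2 and 3: 4 + 12 = 16 planned (16.2), with no field split fixed. 5.4 says only that Cohort 3 may be stratified by field.

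**The case against.** The strongest reply is that this is an omission and not a contradiction. The cap is placed on CTV3 by name, CTV3 is a pelvic sub-region, and the PTV row is headed as a pelvic volume. Nothing forbids a further para-aortic volume. The extended-field sentences in 5.6, 5.7 and 5.7.2 are the more specific text, and a plan stopped at the bifurcation would not be the field that 5.6 describes. An experienced radiation oncologist would see this. That stands as a limit on the practical risk. It does not remove the problem: the table says how the PTV is to be generated, that instruction excludes the para-aortic region, and it applies to IMRT and 3D plans without exception.

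A reader might infer several stronger points that the documents do not support:

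- **A shortfall in millimetres.** It is tempting to set the 3 cm in 5.7.1 against the 5 mm expansion in 5.7.3. The first is a portal border for bone-landmark planning and the second is a PTV edge in a contoured plan. The difference would also rest on an assumed node position. No such figure is given here.
- **CTV3 as the only nodal CTV.** There is also a boost CTV. CTV3 is the only elective one.
- **Gross para-aortic disease left untreated.** The GTV row still requires 45 Gy to all known gross disease. What is missing is the elective target.
- **An error in the boost row.** The row is limited to pelvic nodes, while the nodal boost in 5.7.5 can go to any grossly positive node. The 5.7.5 boost follows the 45 Gy, whereas the table's boost doses match the SIB boost, so the two may describe different treatments.

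**Conclusion.** The point holds for contoured plans. Read as written, the 5.7.3 table gives an extended-field patient a PTV without an elective para-aortic target, contrary to 5.6, 5.7 and 5.7.2, and the protocol does not say which prevails. It should be fixed.

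The size is at most 4 of 24 patients (16.7%) in Cohort 1, plus any extended-field patients with contoured plans among the 16 in Cohorts 2 and 3. Both counts depend on how many plans are contoured, which the protocol does not state. Four-field box treatment without 3D planning is not affected.

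The practical risk is limited if, as is likely, the treating radiation oncologist follows the extended-field text. A reader might go on to infer that the safety stopping rules in 16.1.1 or the planned analyses are compromised. The documents do not support that: no threshold, sample size or estimate changes.

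**What to change.** In 5.7.3:

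1. State that the upper-border cap on CTV3 applies to whole-pelvic plans only.
2. Add an extended-field row for a para-aortic nodal CTV, expanded and fused into the PTV. The radiation oncology lead sets its upper border and margin so that the resulting PTV or field meets 5.7.1 and 5.7.2. The 3 cm in 5.7.1 is a portal border, so it should not be used as a CTV border with an expansion added on top. That could enlarge the irradiated volume in a trial whose primary endpoint is acute toxicity.
3. State in that row the structure from which the 2 cm minimum in 5.7.2 is measured.

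In 5.7.1, change the reference to section 5.2.3 to 5.7.3.

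Leave the boost row as it is. Whether it should reach para-aortic nodes is a separate clinical decision.

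The cost is a wording amendment (one qualified row, one new row, one corrected reference) and a short clinical decision by the radiation oncology lead. It needs no extra patients, visits, procedures or data items.

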5.7.4 Definition of critical structures and margins

The structures marked as “Required” in the table must be contoured and documented with the treatment plan. Structures marked as “Required when applicable” must be contoured and documented only when applicable.

Conventional RT (4-field box)

For a 4-field box treatment without 3D planning, contouring critical structures is not required. For 3D plans, critical structures and margins will be the same as for IMRT described below.

IMRT

Location	Specification
External (Required)	Normal tissues will be contoured on the CT simulation scan. The tissue within the skin surface and outside all other critical normal structures and the PTV should be contoured on every slice and designated as “External.”
Bowel space (Required)	Bowel Space will be contoured beginning from the axial slice situated 1 cm superior to the superior-most slice containing PTV (if bowel is not present at this level, the bowel contour will start from its most superior extent), and will continue to its most inferior extent in the pelvis. The Bowel Space will include the outermost

BrUOG 355: 7/8/17, 7/11/17, 7/20/17, 8/7/17, 8/8/17, 8/14/17, 8/16/17, 8/21/17, 8/22/17, 8/24/17, 8/28/17, 9/5/17, 9/6/17, 9/8/17, 9/11/17, 11/7/17, 11/8/17, 11/19/17 approved DD, 11/20/17, 12/12/17, 12/14/17, 1/29/18, 2/1/18, 2/6/18, 2/7/18, 2/8/18, 2/9/18, 2/12/18, 2/13/18, 3/8/18 all reviews, 3/9/18, 3/13/18, 3/14/18, 3/15/18, 4/19/18, 4/23/18, 5/29/18, 6/5/18, Amendment # 1 7/9/18, Amendment # 2 12/12/18, Amendment #3, 4/6/2020, Amendment #4 5/11/2020

	extent of the bowel loops plus any space within the abdominal cavity the bowel may occupy. Individual loops of bowel should not be contoured separately. Bowel Space will be outlined on each axial CT slice. Rectum should be contoured separately from bowel.
Rectum (Required)	The outer rectal wall will be contoured and filled in, treating the organ as a solid continuous structure, and will be defined from the level of the sigmoid flexure to the anus.
Bladder (Required)	The outer bladder wall will be contoured and filled in, treating the organ as a solid continuous structure.
Bone marrow (Required)	The outer bone contour will be delineated and filled in, treating the bone marrow as a solid continuous structure. The regions contoured will include the os coxae, L4 and L5 vertebral bodies, entire sacrum, acetabulae, and proximal femora. The caudal-most extent of the bone marrow contour should be at the level of the ischial tuberosities.
Active Bone Marrow (Required)	Active or functional BM will be a subset of the entire BM volume (delineated in Bone Marrow), as determined by ¹⁸ F-FDG-PET/CT. Active BM will be defined as the sub region of total BM with a standardized uptake value (SUV) greater than the mean value over the total BM volume. Automatic segmentation using commercially available software will be used to define the functional BM volume, which will be used as an avoidance structure for IMRT planning.
Femur (left and right, separately) (Required)	The outer contours of the left and the right femoral head will be delineated and filled in, treating each separately as its own solid continuous structure. Do not include the femoral neck.

Brachytherapy

Standard	Specification
Bladder (Required)	The outer bladder wall is contoured. Calculated at the center (in the superior-inferior plane on AP view) of a contrast-filled balloon of a Foley catheter and closest to the applicator system on a lateral view.
Rectum (Required)	The outer rectal wall is contoured from above the anal sphincter to the level of transition into the sigmoid.

BrUOG 355: 7/8/17, 7/11/17, 7/20/17, 8/7/17, 8/8/17, 8/14/17, 8/16/17, 8/21/17, 8/22/17, 8/24/17, 8/28/17, 9/5/17, 9/6/17, 9/8/17, 9/11/17, 11/7/17, 11/8/17, 11/19/17 approved DD, 11/20/17, 12/12/17, 12/14/17, 1/29/18, 2/1/18, 2/6/18, 2/7/18, 2/8/18, 2/9/18, 2/12/18, 2/13/18, 3/8/18 all reviews, 3/9/18, 3/13/18, 3/14/18, 3/15/18, 4/19/18, 4/23/18, 5/29/18, 6/5/18, Amendment # 1 7/9/18, Amendment # 2 12/12/18, Amendment #3, 4/6/2020, Amendment #4 5/11/2020

5.7.5 Dose Prescription

Conventional RT

For Conventional RT, the prescription dose of 45 Gy at 1.8 Gy/fraction will be delivered to the isocenter which is defined as the intersection of the four beams. EBRT is preferably given once daily Monday-Friday, for 5 fractions per week. A three consecutive day parametrial boost may be optionally given in the sixth week.

IMRT

Standard	Dose (Gy)	Fraction size (# fractions)	Technique
PTV	45	1.8 (25)	Exactly 95% of PTV receives ≥ 45 Gy
PTV (for SIB)	47.6	1.7 (28)	Exactly 95% of PTV receives ≥ 47.6 Gy
PTV boost (for SIB)	54.0-59.4	1.93-2.12 (28)	Exactly 95% of PTV receives $\geq 54=58.4$ Gy

Parametrial boost.

After the delivery of 45 Gy, at the discretion of the treating physician, a parametrial boost of 5.4 Gy at 1.8 Gy/fraction may be delivered to mid-plane given by AP/PA fields and the center of the unblocked portion of the field.

Lymph Node Boost

After the delivery of 45 Gy WPRT/EFRT +/- parametrial boost, a nodal boost may be delivered to any grossly positive lymph node (PET SUV > 2.5, LN > 15mm short axis diameter on CT/MRI, or histologically positive). Nodal boosts should be delivered to a final dose of 54-59.4 Gy in keeping with bowel tolerance at the discretion of the treating physician.

HDR Brachytherapy

In point-directed approach, the doses of 27.5 - 30 Gy and 35 - 40 Gy will be delivered to the point A for HDR. The HDR brachytherapy dose can be prescribed to a high-risk clinical target volume (CTV) as volume-directed approach, but point A dose must be documented.

Total EBRT (Gy)	# Fractions	HDR Point A dose/fraction (Gy)	Total HDR point A Dose (Gy)	Total Point A EQD2-Gy ₁₀
45	4	7	28	83.9
45	5	5.5	27.5	79.8
45	5	6	30	84.3
47.6	4	7	28	86.1
47.6	5	5.5	27.5	81.9
47.6	5	6	30	86.4

HDR-Point A determined implant or volume directed approach

BrUOG 355: 7/8/17, 7/11/17, 7/20/17, 8/7/17, 8/8/17, 8/14/17, 8/16/17, 8/21/17, 8/22/17, 8/24/17, 8/28/17, 9/5/17, 9/6/17, 9/8/17, 9/11/17, 11/7/17, 11/8/17, 11/19/17 approved DD, 11/20/17, 12/12/17, 12/14/17, 1/29/18, 2/1/18, 2/6/18, 2/7/18, 2/8/18, 2/9/18, 2/12/18, 2/13/18, 3/8/18 all reviews, 3/9/18, 3/13/18, 3/14/18, 3/15/18, 4/19/18, 4/23/18, 5/29/18, 6/5/18, Amendment # 1 7/9/18, Amendment # 2 12/12/18, Amendment #3, 4/6/2020, Amendment #4 5/11/2020

In general, HDR insertions should start during the fourth week and be separated by a minimum of 48 hours and no more than 2 insertions should be performed per week. Iridium-192 is the preferred source for HDR brachytherapy. External beam radiation and brachytherapy may not be administered on the same day. Radiation therapy must be completed within 6 weeks of its initiation.

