5.7 Radiation specifications

This protocol requires photon external beam radiation therapy (EBRT), either 3D conventional radiation therapy (3D- CRT) or intensity modulated radiation therapy (IMRT) techniques followed by low dose rate (LDR) or high dose rate (HDR) brachytherapy. Radiation therapy must be completed within 60 days of initiation. Four-field box 3D-CRT and IMRT are pretreatment stratification variables.

- For 3D-CRT, the prescription dose is 45 Gy in 25 fractions at 1.8 Gy/fraction with an optional parametrial boost of 5.4 Gy in three fractions at 1.8 Gy/fraction. EBRT should be given once daily Monday-Friday, 5 fractions per week.
- For IMRT, the prescription dose is 45 Gy in 25 fractions at 1.8 Gy/fraction, unless a simultaneous integrated boost (SIB) is used for gross nodal disease. For SIB cases, the primary target will receive 47.6 Gy in 1.7 Gy/fraction and the gross nodal PTV (PTV_Boost) will receive 1.93-2.12 Gy per fraction, depending on bowel tolerance. IMRT should be given once daily Monday-Friday, 5 fractions per week.
- For brachytherapy, the prescription doses are 27.5 - 30 Gy for HDR.

Cohort 1A - Extended-Field Radiation Therapy (EFRT) - EFRT will be used for patients with any positive common iliac LN requiring extension of the superior border of the radiation field above the L4-L5 inter-space as detailed in Section 5.7.1.

Cohort 1B -Whole Pelvic Radiation Therapy (WPRT) - WPRT will be used for patients without evidence of high common iliac LN necessitating EFRT. The traditional whole pelvic radiation field borders are as detailed in Section 5.7.1.

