For patients who underwent lymph node dissection: If clips are present to document the position of the lymph nodes, these should be used as a guide when anterior blocks are designed to shield small bowel. When shielding bowel, at least 3 cm should not be blocked anterior to the L4 and L5 vertebral bodies in order to adequately encompass the low para-aortic region.

IMRT

IMRT plans may include static field arrangements (e.g. 5-9 fields), modulated arc therapy, or Tomotherapy. Pseudo-step-wedge intensity modulation (PSWIM) or volumetric modulated arc therapy (VMAT) techniques are permitted. IMRT should use 6-15 MV photons.

Parametrial boost

After conventional RT or IMRT delivery, a parametrial boost can be delivered at the treating

BrUOG 355: 7/8/17, 7/11/17, 7/20/17, 8/7/17, 8/8/17, 8/14/17, 8/16/17, 8/21/17, 8/22/17, 8/24/17, 8/28/17, 9/5/17, 9/6/17, 9/8/17, 9/11/17, 11/7/17, 11/8/17, 11/19/17 approved DD, 11/20/17, 12/12/17, 12/14/17, 1/29/18, 2/1/18, 2/6/18, 2/7/18, 2/8/18, 2/9/18, 2/12/18, 2/13/18, 3/8/18 all reviews, 3/9/18, 3/13/18, 3/14/18, 3/15/18, 4/19/18, 4/23/18, 5/29/18, 6/5/18, Amendment # 1 7/9/18, Amendment # 2 12/12/18, Amendment #3, 4/6/2020, Amendment #4 5/11/2020

physician's discretion. The parametrial boost will use an AP/PA field arrangement. The superior border should be reduced to include only the true pelvis and the upper border of the true pelvis is defined as 1 cm above the inferior aspect of the sacroiliac joint. The inferior border remains the same as in the pelvis fields. A parametrial central field block is a minimum of 4 cm wide.

Brachytherapy

Patients will be treated using HDR brachytherapy for all patients treated on this protocol. Tandem and ring or tandem and ovoids will be used for intact cervix brachytherapy. Interstitial brachytherapy such as with a Vienna applicator is allowed at the discretion of the treating physician. A tandem and cylinder or tandem alone is allowed only for patients where tandem and ring or ovoid application is not possible due to extent of disease or poor anatomy (e.g., obliterated fornices).

Use of IMRT or other external beam techniques in place of brachytherapy to boost gross cervical disease is discouraged. If deemed necessary or essential for the patient's care (e.g., if a patient refuses brachytherapy), reasons for not performing brachytherapy should be documented.

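### Section 5.7.5 assigns two different dose ranges to point A for HDR brachytherapy, against 5.7, 5.7.3 and its own table, and the sections disagree on whether LDR is allowed

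*Combined protocol and SAP*

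**What the plan says.** All references are to the combined protocol and SAP.

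**Dose**
- Section 5.7.5, HDR paragraph, point-directed approach: "the doses of 27.5 - 30 Gy and 35 - 40 Gy will be delivered to the point A for HDR". Both ranges carry the same modality label and the same reference point, and nothing says when each applies.
- Section 5.7: "For brachytherapy, the prescription doses are 27.5 - 30 Gy for HDR". There is no second range.
- Section 5.7.3, volume-directed table: "Required dose = 27.5-30 Gy".
- Section 5.7.5, table below the HDR paragraph: six rows pairing 45 or 47.6 Gy of external beam with 4 × 7, 5 × 5.5 or 5 × 6 Gy. HDR totals are 28, 27.5 and 30 Gy, and each row has an EQD2.

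The 35 to 40 Gy range appears once in the protocol, with no fractionation and no EQD2 attached.

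**Modality**
- Section 5.7 requires external beam "followed by low dose rate (LDR) or high dose rate (HDR) brachytherapy", and section 5.4 lists both modalities for cohorts 1A and 1B.
- Section 5.7.1: "Patients will be treated using HDR brachytherapy for all patients treated on this protocol".
- No section gives a dose labelled LDR.

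**The concern.** Section 5.7.5 is where a site would look for the prescription, and its sentence is worded as an instruction. Read literally, it lets a second, higher HDR range stand beside the one used everywhere else. A site using LDR, as 5.4 and 5.7 allow, finds no dose labelled for it.

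The statistical stake is the primary endpoint. Section 16.1 makes acute toxicity of the combination the primary endpoint. Section 16.1.1 calls treatment not feasible if more than 2 patients in cohort 1 (planned 8) or more than 1 in cohort 2 (planned 4) have a grade 3 or higher event lasting 14 days or longer. That count does not require attribution to nivolumab. Section 5.3 gives every patient nivolumab before chemoradiation, so no cohort is free of it to show what a change in radiation dose would do alone. With counts this small, one or two patients treated at a different brachytherapy dose could move a cohort across its limit.

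**Working it through.** **Inputs**
- External beam: 45 Gy at 1.8 Gy per fraction, or 47.6 Gy at 1.7 Gy per fraction (5.7 and 5.7.5).
- HDR schedules: 4 × 7, 5 × 5.5 and 5 × 6 Gy (5.7.5 table).
- Alpha/beta: 10 Gy, from the subscript in the table's EQD2 column heading.

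**Formula.** EQD2 = D × (d + 10)/(2 + 10), where D is total dose and d is dose per fraction, summed over external beam and HDR.

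**Step 1: reproduce the plan's table**
- External beam: 45 × 11.8/12 = 44.25 Gy; 47.6 × 11.7/12 = 46.41 Gy.
- HDR: 28 × 17/12 = 39.67 Gy; 27.5 × 15.5/12 = 35.52 Gy; 30 × 16/12 = 40.00 Gy.

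| External beam (Gy) | HDR schedule | Sum (Gy) | Table (Gy) |
|---|---|---|---|
| 45 | 4 × 7 | 83.92 | 83.9 |
| 45 | 5 × 5.5 | 79.77 | 79.8 |
| 45 | 5 × 6 | 84.25 | 84.3 |
| 47.6 | 4 × 7 | 86.08 | 86.1 |
| 47.6 | 5 × 5.5 | 81.93 | 81.9 |
| 47.6 | 5 × 6 | 86.41 | 86.4 |

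All six rows reproduce. The table is arithmetically consistent, so the conflict lies between the sentence and the other statements.

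**Step 2: read 35 to 40 Gy as physical HDR dose.** No fractionation is given, so the number of fractions is an assumption. With 45 Gy external beam:
- 5 fractions: 35 × 17/12 = 49.58, total 93.8 Gy; 40 × 18/12 = 60.00, total 104.3 Gy.
- 4 fractions: 35 × 18.75/12 = 54.69, total 98.9 Gy; 40 × 20/12 = 66.67, total 110.9 Gy.
- 6 fractions, lower end: 35 × 15.83/12 = 46.18, total 90.4 Gy.

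The range is therefore about 94 to 104 Gy in 5 fractions and about 90 to 111 Gy over 4 to 6. The table has 79.8 to 84.3 Gy with 45 Gy external beam and at most 86.4 Gy in any row. Six fractions appears nowhere in the table and only widens the range shown.

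**Step 3: read 35 to 40 Gy as EQD2.** Step 1 gives the HDR component of the tabulated schedules as 35.5, 39.7 and 40.0 Gy. That nearly matches the second range. On this reading it restates the same schedules in other units, and the excess is zero.

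**Step 4: read it as an LDR range.** Sections 5.4 and 5.7 name LDR without a dose, so an LDR label may have dropped out of the sentence. The HDR calculation in step 2 would then not apply, and the conflict with 5.7.1 on modality would remain.

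**The case against.** The strongest reply is that no careful site would go wrong. The range conflicting with the rest appears once, without a schedule. Complete schedules stand directly below it, and 5.7 and 5.7.3 agree with them. Delivering 35 to 40 Gy as HDR would require a fractionation that the protocol does not supply. The EQD2 match in step 3 also offers a harmless explanation. This lowers the likelihood of a dosing difference, but leaves an instruction that cannot be reconciled with the text around it. The harmless readings also imply different corrections: one makes the range an LDR prescription, the other makes it no prescription at all. The documents do not choose between them.

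Four stronger inferences are tempting, and the documents do not support them:
- **That patients were given inconsistent or higher doses.** The documents contain no delivery data; this is a foreseeable risk only.
- **That 90 to 111 Gy is the size of the problem.** That holds only if the range is physical HDR dose. A fair range starts at no excess.
- **That extra toxicity would necessarily be put down to nivolumab.** Section 8.8 asks for serious-event causality for nivolumab, cisplatin and radiation. Section 11, note N, asks for a summary of all radiation given, and 5.7.5 requires the point A dose to be documented when a volume is prescribed. A different delivered dose should be traceable. The feasibility count in 16.1.1 nevertheless ignores attribution, so an effect on that decision remains possible.
- **That both ranges are given in succession**, which would total 62.5 to 70 Gy (27.5 + 35 to 30 + 40). No row of the table and no other section points to this.

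**Conclusion.** The contradiction in the text is certain: one sentence in 5.7.5 conflicts with 5.7, 5.7.3 and every row of the table below it, and the modality statements in 5.4 and 5.7 conflict with 5.7.1. It is an inconsistency of wording; nothing in the table is miscalculated.

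The size is conditional. With alpha/beta of 10 Gy and 45 Gy external beam, it runs from no excess (EQD2 reading) to about 94 to 104 Gy in an assumed 5 fractions, or about 90 to 111 Gy over an assumed 4 to 6 (physical HDR reading), against 79.8 to 84.3 Gy tabulated. On the LDR reading this comparison does not apply. If a site followed the literal reading, delivered dose could differ between patients and affect both the acute-toxicity endpoint and the feasibility count.

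It must be fixed because it is operative dosing text in a trial whose primary endpoint is toxicity. That conclusion does not depend on which end of the range is true.

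**What to change.** The sponsor, with the radiation oncology lead, should reconcile sections 5.4, 5.7, 5.7.1, 5.7.3 and 5.7.5 (sentence and table) so that one consistent set of modality, dose and fractionation statements appears throughout. Every dose range should be labelled by modality and as physical dose or EQD2. If more than one range or modality is meant to remain, the text should state when each applies and give its schedule. Which dose or modality stands is for the sponsor to decide; none is proposed here.

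The cost is a protocol wording amendment. It changes neither the sample size nor the analysis methods.
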